9.4. Urine pregnancy tests

The investigator or designee will perform a urine pregnancy test for subjects who are WOCBP at Visit 1, at Visit 2 prior to randomization and at Visit 8.

Subjects who are WOCBP must have a negative pregnancy test result at Visit 1 to continue in the study and at Visit 2 to be randomized.

If the result of any post-randomization urine pregnancy test is positive, the subject will be withdrawn from the study and the subject's pregnancy documented and followed as outlined in Section 11.

9.5. Other Evaluations

9.5.1. Demographics and medical history

At Visit 1, the investigator or designee will collect demographic information including date of birth, sex at birth, race and, if appropriate, ethnicity for each subject.

At Visit 1, the investigator must determine each subject's Fitzpatrick skin type and document appropriately on the subject's CRF.

Table 5 Fitzpatrick Skin Type Scoring System

Skin Type Classification	Description
Type I	always burns, never tans (pale white; blond or red hair; blue eyes; freckles)
Type II	usually burns, tans minimally (white; fair; blond or red hair; blue, green, or hazel eyes)
Type III	sometimes mild burn, tans uniformly (cream white; fair with any hair or eye color)
Type IV	burns minimally, always tans well (moderate brown)
Type V	very rarely burns, tans very easily (dark brown)
Type VI	Never burns, never tans (deeply pigmented dark brown to darkest brown)

(Fitzpatrick 1988)

Medical history information will be recorded including all medical conditions and disease states that, at Visit 1:

- Are ongoing
- Require concomitant therapy
- Are, in the opinion of the investigator, relevant to the subject's study participation.

9.5.2. Standardized photography

At Visits 1, 2, 4, 6, 7 and 8, a qualified investigational center staff member, other than the investigator, will take standardized color photographs of each Target Lesion.

The photographs are to document the location of the Target Lesion and to assist with relocating the Target Lesion and the Target Lesion ID stickers must be visible in the photographs (Section 8.1). The subject's identity will not be revealed in the study photographs.

At Visit 2, the photographs must be taken prior to the study medication treatment. Care must be taken to ensure the same lighting, background, subject positioning relative to the camera and camera settings are used for each photograph.

Equipment, supplies, training and detailed instructions for obtaining and managing the photographs will be provided to the investigational center prior to the initiation of subject enrollment.

10. ADVERSE EVENTS

10.1. Definitions

10.1.1. Adverse events (AE)

- An adverse event (AE) is any untoward medical occurrence in a patient that develops or worsens in severity during the conduct of a clinical study of a pharmaceutical product and does not necessarily have a causal relationship to the study drug. An adverse event can, therefore, be any unfavorable and unintended physical sign, symptom, or laboratory parameter that develops or worsens in severity during the course of the study, or significant worsening of the disease under study (or any concurrent disease), whether or not considered related to the study drug. Accordingly, an adverse event could include any of the following:
- intercurrent illnesses
- physical injuries
- events possibly related to concomitant medication
- significant worsening (change in nature, severity, or frequency) of the disease under study or other pre-existing conditions. (NOTE: A condition, recorded as pre-existing, that is intermittently symptomatic [e.g., headache] and which occurs during the study should be recorded as an adverse event.)
- drug interactions
- events occurring during diagnostic procedures or any washout phase of the study
- laboratory or diagnostic test abnormalities occurring after the start of the study (i.e., after screening and once confirmed by repeat testing) that results in the withdrawal of the patient from the study, requires medical treatment or further diagnostic work-up, or is considered by the study investigator to be clinically significant. NOTE: Abnormal laboratory test results at the screening visit that preclude a patient from entering the study or receiving study treatment are not considered adverse events, but will be recorded to monitor data from patients who do not meet screening criteria.

Worsening of any of the Target Lesion assessments should be reported as an AE ONLY if the use of the study medication is interrupted or discontinued or if therapy is required to manage the event.

The investigator must, for any Target Lesion related AE, question the subject in detail to determine if there are any confounding factors (e.g., irritation by clothing or activity, sunburn) for any such AE.

The investigator should, when certain, report a diagnosis rather than the signs, symptoms or clinically relevant abnormal laboratory values associated with the AE. Otherwise, signs, symptoms or abnormal laboratory values may be used to describe the AE.

Any CS abnormality discovered prior to the first study medication treatment should be reported as medical history, not as an AE.

10.1.2. Serious adverse event (SAE)

A Serious Adverse Event is any untoward medical occurrence that at any dose:

- Results in death
- Is life threatening
- Requires inpatient hospitalization or prolongation of existing hospitalization
- Results in persistent or significant disability/incapacity,
- Is a congenital anomaly/birth defect or
- Is an important medical event.

The term “life threatening” refers to an event in which the subject was at risk of death at the time of event; it does not refer to an event that hypothetically might have caused death if it was more severe.

Inpatient hospitalization is considered to have occurred if the subject is admitted to the hospital on an in-patient basis, even if released the same day. Prolongation of hospitalization is defined as an additional night stay in the hospital. Hospitalization for elective treatment of a pre-existing condition that did not worsen from baseline is not considered an AE.

Important medical events are those that may not be immediately life threatening, result in death or hospitalization, but are clearly of major clinical significance and may jeopardize the subject or require intervention to prevent one of the outcomes listed in the SAE definition above. These should also usually be considered serious. Examples of such events are intensive treatment in an emergency room or at home for allergic bronchospasm, blood dyscrasia or convulsions that do not result in hospitalization.

10.1.3. Adverse event reporting period

The investigator must start reporting non-serious AEs starting with the subject’s first study medication treatment continuing until Visit 5. Non-serious adverse events that occur between the time the subject was consented and the first application of study medication will be reported as medical history.

Reporting for SAEs begins after the subject signs the informed consent and continues until Visit 6 (regardless of relationship to study medication). If a subject experiences a SAE after Visit 6 that is deemed by the investigator to be related to study medication, the investigator must report this to the Sponsor using the study specific SAE report form.

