¹⁷The reporting period for Serious Adverse Events (SAEs) begins when the subject signs the informed consent and continues through Visit 6. Refer to Section 10.1.2 for instructions on the reporting of SAEs. Non-serious clinical adverse events will be collected following the application of the study medication at Visit 2. Non-serious adverse events that occur between the time of consent and study medication application will be documented as medical history. All safety reporting (AEs and SAEs) will conclude at Visit 6 (approximately 21 days after last study medication application) except for clinical adverse events related to local skin reactions. These events will be collected through V8.

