9.2. Vital signs

Vital signs will be measured by a qualified staff member at Visit 1, Visit 2 prior to randomization, and at Visit 8. The following items will be measured:

- Body temperature
- Pulse rate
- Respiration rate
- Blood pressure (systolic and diastolic) after the subject sits quietly for at least 5 minutes
- Height (at Visit 1 only)
- Weight (at Visit 1 only).

Any measure that is, in the opinion of the investigator, abnormal AND clinically significant (CS must be recorded as history if found prior to the first study medication treatment or as an AE if found after the first study medication treatment begins (Section 10.1).

A systolic blood pressure >140mm Hg or a diastolic blood pressure >90mm Hg is considered abnormal and therefore must be defined as CS or not clinically significant (NCS) on the CRFs.

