10.2. Reporting Procedures

10.2.1. Procedures for reporting adverse events

At each post enrollment visit, the investigator or designee will question the subject to elicit AEs using a non-directive question such as “Has there been any change in your health since the previous study visit?”

The investigator or designee will monitor the subject for at least 20 minutes after the Treatment Completion Time at Visit 2 and at Visit 4 to elicit AEs in a similar manner.

If appropriate, based on the subject's response to non-directed questioning regarding AEs, the investigator or designee will follow-up with directed questions and appropriate evaluations.

Any AE noted during the reporting period must be reported in the source documents and on the appropriate AE CRF.

AEs that are defined as “Not Related” to the study medications will be followed until they are resolved or until the subject’s last study visit. AEs that are defined as “Related” to the study medications will be followed until they are resolved or, if not resolved after the subject’s last study visit, until in the opinion of the investigator, the AE reaches a clinically stable outcome with or without sequelae.

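### The adverse event reporting period ends at Visit 5 in Section 10.1.3 and at Visit 6 in Table 1 and footnote 17, and footnote 17 closes it before the Visit 8 findings that Sections 9.2 and 9.3 class as AEs

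*Combined protocol and SAP*

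**What the plan says.** - **Section 10.1.3** sets the period for non-serious AEs as running from the "first study medication treatment continuing until Visit 5". SAEs are reported from consent to Visit 6. A later duty is added: "If a subject experiences a SAE after Visit 6 that is deemed by the investigator to be related to study medication", the investigator must still report it. There is no exception for skin reactions.
- **Section 6, Table 1** marks the AE row at Visits 2 to 6 and leaves Visits 7 and 8 blank.
- **Section 6, footnote 17** states: "All safety reporting (AEs and SAEs) will conclude at Visit 6 (approximately 21 days after last study medication application"). It then makes one exception: "except for clinical adverse events related to local skin reactions. These events will be collected through V8".
- **Section 10.2.1** requires AE questioning throughout: "At each post enrollment visit, the investigator or designee will question the subject to elicit AEs". The recording duty is narrower: "Any AE noted during the reporting period must be reported in the source documents and on the appropriate AE CRF".
- **Section 9.2** gives the vital-sign schedule: "Vital signs will be measured by a qualified staff member at Visit 1, Visit 2 prior to randomization, and at Visit 8". An abnormal and clinically significant value is to be recorded "as an AE if found after the first study medication treatment begins (Section 10.1"). **Section 9.3** applies the same rule to laboratory results, which are sampled at Visits 1 and 8 only.
- **Section 12.3** tabulates the proportion of subjects with treatment-emergent AEs by treatment and System Organ Class, without inferential testing. The **Synopsis** leaves the detail of the safety endpoints to an SAP.

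**The concern.** The protocol gives two end dates for the same obligation and no rule for choosing between them. Section 10.1.3 is the section headed as the reporting period, while Table 1 is what sites work from at each visit. With approximately 9 centers, different sites could reasonably follow different texts.

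Footnote 17 also conflicts with instructions elsewhere. Read literally, it stops AE reporting before the only scheduled visit at which a post-treatment laboratory or vital-sign AE can be detected. It also stops SAE reporting at a point after which Section 10.1.3 still requires related SAEs to be reported.

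What is at stake is which AEs are recorded and how they are classified, and so the completeness of the Section 12.3 tables. Safety is part of the primary objective in Section 3.2.1 and a secondary objective in Section 3.2.2. An SAP can choose an analysis window afterwards, but only among events that were recorded.

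**Working it through.** **Inputs (Table 1).** Windows are counted from the nominal day, which is an assumption, and visits are taken as free to fall anywhere in their windows.

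| Visit | Nominal day | Window | Earliest to latest |
|---|---|---|---|
| 2 (treatment) | 1 | none | 1 |
| 4 (possible retreatment) | 22 | +4 | 22 to 26 |
| 5 | 29 | +7 | 29 to 36 |
| 6 | 50 | ±7 | 43 to 57 |
| 8 | 106 | ±7 | 99 to 113 |

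Formulas: nominal interval = later day − earlier day; shortest = earliest later visit − latest earlier visit; longest = latest later visit − earliest earlier visit.

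**The plan's own figure.** Footnote 17 puts Visit 6 at about 21 days after the last application.

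- Retreated at Visit 4: 50 − 22 = 28 days; range 43 − 26 = 17 to 57 − 22 = 35.
- Not retreated: 50 − 1 = 49 days; range 43 − 1 = 42 to 57 − 1 = 56.

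So 21 days is attainable within the windows for a retreated subject, but it is not the scheduled interval. The Visit 5 to Visit 6 gap happens to be 21 days; the documents do not say whether that is where the figure comes from.

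**Visit 5 against Visit 6 as the cut-off.**

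| Interval | Nominal | Range |
|---|---|---|
| Visit 5 to Visit 6 | 50 − 29 = 21 | 43 − 36 = 7 to 57 − 29 = 28 |
| Visit 4 to Visit 5 | 29 − 22 = 7 | 29 − 26 = 3 to 36 − 22 = 14 |
| Visit 4 to Visit 6 | 28 | 17 to 35 |

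The latest Visit 5 is Day 36 and the earliest Visit 6 is Day 43, so no use of the windows brings the cut-offs together.

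**Distance to the Visit 8 findings.**

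| Interval | Nominal | Range |
|---|---|---|
| Visit 6 to Visit 8 | 106 − 50 = 56 | 99 − 57 = 42 to 113 − 43 = 70 |
| Visit 5 to Visit 8 | 106 − 29 = 77 | 99 − 36 = 63 to 113 − 29 = 84 |

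Both cut-offs precede Visit 8 by weeks. They do not conflict with Sections 9.2 and 9.3 in the same way, however. Section 10.1.3 sets a period of mandatory reporting and does not forbid later reporting. Footnote 17 says reporting concludes, and its single exception does not cover laboratory or vital-sign findings. The direct conflict is therefore with footnote 17.

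**Exceptions set side by side.**

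| Event | Section 10.1.3 | Footnote 17 | Table 1 AE row |
|---|---|---|---|
| Skin-reaction AE after Visit 6 | not mentioned | collected to Visit 8 | blank at Visits 7 and 8 |
| Related SAE after Visit 6 | must be reported | reporting concluded | blank |
| Clinically significant Visit 8 laboratory or vital-sign finding | not mentioned | reporting concluded | blank |

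**Does another section settle it?** No. Section 10.2.1 ties recording to the reporting period, which is the term in dispute. Section 10.2.2 ties the SAE procedure to the same term. The opening of Section 9 speaks of AE reporting over the whole study, which is yet another version.

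**The case against.** The strongest reply is that Section 10.1.3 sets a minimum. A site that records through Visit 6 satisfies both it and Table 1, so the contrast of 7 against 28 days arises only if a site disregards the schedule. The CRFs, which are not in the documents, might settle practice. This narrows the risk but does not remove it: Section 10.1.3 is headed as the reporting period, and Section 10.2.1 obliges sites to record only within that period.

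On Visit 8, Sections 9.2 and 9.3 give specific, mandatory instructions that a site may reasonably put ahead of a general footnote. Section 10.1.1 also counts clinically significant laboratory abnormalities as AEs. Loss of these findings is therefore possible but not shown. The results are in any case collected and graded for clinical significance, and Section 12.3 tabulates vital signs and clinically relevant abnormal laboratory results.

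On SAEs, a routine close with a continuing duty for related events is coherent within Section 10.1.3, and the footnote may simply be an incomplete summary. That lowers the weight of this item; the two texts still differ.

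Several points stand as limits:

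- The 21-day figure is approximate, and the cut-off is defined by visit, so no site action depends on it.
- The blank cells at Visits 7 and 8 carry little weight, since that row refers to footnote 17.
- Questioning at every visit is needed anyway to follow open AEs, so Section 10.2.1 is not a contradiction in itself. It only fails to resolve one.
- Skin reactions are graded at Visits 2 to 8 regardless, and Section 10.1.1 restricts when worsening of a Target Lesion counts as an AE, so late skin-reaction AEs may be few.
- AEs already recorded are followed to the last visit, and beyond it if related and unresolved.
- The rule is the same in all three arms of a double-blind study, so no direction of bias is shown.

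**Conclusion.** The concern holds. The end of non-serious AE reporting is stated as Visit 5 in one place and Visit 6 in another, 21 nominal days apart (7 to 28 with windows), with no rule of precedence. Footnote 17, read as written, also contradicts Sections 9.2 and 9.3 on Visit 8 findings and Section 10.1.3 on later related SAEs.

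The consequence is possible incompleteness of late AEs in descriptive tables, mainly new non-serious events after Visit 5. The documents do not allow the number of such events to be estimated. The ranges rest on reading the Table 1 windows from the nominal day; the nominal gaps do not depend on that assumption. The plan should be corrected, but the point does not threaten the efficacy analysis.

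**What to change.** Reconcile Table 1, footnote 17 and Sections 9.2, 9.3, 10.1.3 and 10.2.1 to one AE reporting period, with the same explicit exceptions wherever it is described. Two forms would be coherent:

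- record AEs through Visit 8, and mark Visits 7 and 8 in the AE row of Table 1; or
- keep one earlier cut-off, with stated exceptions for skin-reaction AEs, related SAEs, and clinically significant Visit 8 laboratory and vital-sign findings.

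Use the chosen period to define treatment-emergent AEs in Section 12.3 and in the SAP. Reconcile the 21-day figure in footnote 17 with the visit schedule; the documents do not show whether the visit or the interval was intended.

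The cost is protocol wording. Recording through Visit 8 adds some AE processing but no new questioning, because Section 10.2.1 already requires it at every post-enrollment visit. An earlier cut-off with stated exceptions adds wording only.

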10.1.4. Severity

The investigator must define the severity of each AE using the following definitions as a guideline. The investigator will consider the range of the possible severity of the event and identify the severity that is the most appropriate according to her/his medical judgment.

Mild – Awareness of signs or symptom, but easily tolerated

Moderate – Discomfort, enough to cause interference with usual activity

Severe – Incapacitating with inability to perform usual activity.

10.1.5. Relationship to study medication

The investigator will determine if there is a reasonable causal relationship between the study medication and an AE or not. The investigator will use her/his best medical judgment and consider all relevant factors (*e.g.*, temporal relationship, location of the event, the subject's relevant medical history, concomitant therapies and concurrent conditions) to determine the relationship of the AE to the study medication. The investigator will define the relationship of an AE to the study medication by selecting one of the following categories:

Related – There is a reasonable possibility that there is a causal relationship between the study medication and the AE.

Not Related – There is not a reasonable possibility that there is a causal relationship between the study medication and the AE.

The term “reasonable causal relationship” means there are facts or arguments to suggest a causal relationship (International Conference on Harmonization (ICH) E2A).

10.2. Reporting Procedures

10.2.1. Procedures for reporting adverse events

At each post enrollment visit, the investigator or designee will question the subject to elicit AEs using a non-directive question such as “Has there been any change in your health since the previous study visit?”

The investigator or designee will monitor the subject for at least 20 minutes after the Treatment Completion Time at Visit 2 and at Visit 4 to elicit AEs in a similar manner.

If appropriate, based on the subject's response to non-directed questioning regarding AEs, the investigator or designee will follow-up with directed questions and appropriate evaluations.

Any AE noted during the reporting period must be reported in the source documents and on the appropriate AE CRF.

AEs that are defined as “Not Related” to the study medications will be followed until they are resolved or until the subject’s last study visit. AEs that are defined as “Related” to the study medications will be followed until they are resolved or, if not resolved after the subject’s last study visit, until in the opinion of the investigator, the AE reaches a clinically stable outcome with or without sequelae.

10.2.2. Procedure for reporting a serious adverse event

Upon becoming aware of a SAE occurring during the AE reporting period, whether or not related to the study medications, the investigator must:

1. Take the appropriate medical action to ensure the subject’s safety
2. Immediately inform the Medical Monitor of the SAE:

[name]
Aclaris Therapeutics, Inc.
[name]
[name]
[name]
[contact]
Serious Adverse Event [contact]
Email: [contact]

3. Within 24-hours of becoming aware of the event, a SAE report form, an AE CRF and any other relevant information (*e.g.*, concomitant medication CRF, medical history CRF, laboratory test results) must be faxed to the SAE Fax line listed above.
4. Monitor and document the progress of the SAE until it resolves or, if not resolved after the subject’s last study visit, until in the opinion of the investigator the AE reaches a clinically stable outcome with or without sequelae AND the investigator and Medical Monitor agree that the SAE is satisfactorily resolved.
5. Inform the Medical Monitor of SAE updates by telephone followed by an SAE form update sent by fax or by e-mail.
6. Comply with the appropriate regulatory requirements and Aclaris Therapeutics, Inc. instructions regarding reporting of the SAE to the responsible Institutional Review Board (IRB) or Ethics Committee (EC).

10.2.3. Withdrawal Due to an Adverse Event

Any patient who experiences an adverse event may be withdrawn from study drug at any time at the discretion of the investigator. If a patient is withdrawn wholly or in part because of an adverse event, both the adverse events page and termination page of the CRF will be completed at that time. The patient will be monitored until the event has resolved or stabilized, until a determination of a cause unrelated to the study drug or study procedure is made, or until the patient is referred to the care of a local health care professional. The investigator must inform

the medical monitor as soon as possible of all patients who are being considered for withdrawal due to adverse events. Additional reports must be provided when requested.

